### 6.2.2. Treatment Period (Week 1 to Week 16)

The treatment period begins with the administration of study drug and the study procedures are allocated on Treatment Visits 1 (Week 1 [Day 1]), 2 (Week 2 [Day 14 ± 3 days]), 3 (Week 4 [Day 28 ± 3 days]), 4 (Week 6 [Day 42 ± 3 days]), 5 (Week 8 [Day 56 ± 3 days]), 6 (Week 10 [Day 70 ± 3 days]), 7 (Week 12 [Day 84 ± 3 days]), 8 (Week 14 [Day 98 ± 3 days]) and 9 (Week 16 [Day 112±3 days]). The patients will be outpatient during the treatment period. Please refer [Section 19.1](#) for overall activities planned for the treatment period.

#### 6.2.2.1. Treatment Visit 1 (Week 1 [Day 1])

The treatment Visit 1 is planned on Day 1. Following activities are planned for the visit:

- Confirm patient's eligibility prior to randomization
- Review and record patient's prior and concomitant medications
- Perform drugs of abuse screen pre-dose
- Record patient's body weight
- Calculate BMI
- Perform symptom-directed physical examination
- Perform vital signs (systolic/diastolic BP, heart rate, temperature, respiratory rate) evaluation pre-dose
- Perform AUDIT-C
- Randomization
- Pruritus assessment
- AE monitoring
- Perform clinical laboratory analysis including haematology, serum chemistry panel (including liver safety testing: ALT, AST, Alkaline Phosphatase, Gamma Glutamyl Transferase (GGT), Total Bilirubin and Albumin), coagulation tests and lipid and metabolic profile
- Perform urine pregnancy test (for WOCBP only)
- Perform Dipstick urinalysis for all male and female patients
- Perform 12-Lead ECG
- Sampling for analysis of HBV response markers

---

 For positive HCV antibody-test results only, a PCR-based quantitative HCV viral load assessment will also be performed.

 All subjects must have the blood samples collected at pre-dose for quantitative HBV tests: HBsAg, HBV-DNA, HBV-pgRNA, HBcrAg and HBeAg (the later only for anti-HBe positives subjects).

- PD biomarker sampling
- Liver fibrosis and inflammation assessment
- PK Sampling
- Dispense patient diary and explain use
- Dispense EYP001a or placebo and NA (choice between ETV or TFV is at the Investigator discretion)

6.2.2.2. *Treatment Visit 2 (Week 2 [Day 14 ± 3 days])*

The treatment Visit 2 is planned on Day 14 ± 3 days in Week 2. Following activities are planned for the visit:

- Review and record patient's prior and concomitant medications
- Perform vital signs (systolic/diastolic BP, heart rate, temperature, respiratory rate) evaluation pre-dose
- Pruritus assessment
- AE monitoring
- Perform clinical laboratory analysis only liver safety testing: ALT, AST, ALP, GGT, total bilirubin, thrombocytes and albumin
- Sampling for analysis of HBV response markers
- PD biomarker sampling
- PK Sampling
- Review returned patient diary and dispense new diary
- Collect used/unused study drug and assess compliance

6.2.2.3. *Treatment Visit 3 (Week 4 [Day 28 ± 3 days])*

The treatment Visit 3 is planned on Day 28 ± 3 days in Week 4. Following activities are planned for the visit:

- Review and record patient's prior and concomitant medications
- Record patient's body weight
- Calculate BMI
- Perform symptom-directed physical examination
- Perform vital signs (systolic/diastolic BP, heart rate, temperature, respiratory rate) evaluation pre-dose
- Pruritus assessment
- AE monitoring
- Perform clinical laboratory analysis including haematology, serum chemistry panel, coagulation tests, lipid and metabolic profile and TSH.
- Perform urine pregnancy test (for WOCBP only)
- Perform Dipstick urinalysis for all male and female patients
- Perform 12-Lead ECG
- Sampling for analysis of HBV response markers
- PD biomarker sampling
- Liver fibrosis and inflammation assessment
- PK Sampling
- Review returned patient diary and dispense new diary
- Dispense NA
- Collect used/unused study drug and assess compliance

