#### 2.2.2. Secondary Endpoints

- Efficacy assessed as:
  - HBsAg responder rate (decrease from baseline  $\geq 1.0$  on the  $\log_{10}$  scale) at Week 16 of treatment and Weeks 20, 28 and 40 of follow up.
  - HBsAg responder rate (decrease from baseline  $\geq 0.5$  on the  $\log_{10}$  scale) at Weeks 12 and 16 of treatment and Weeks 20, 28 and 40 of follow up.
  - HBsAg loss rate (% patients with HBsAg < LLOQ) at Week 16 of treatment and Weeks 20, 28 and 40 of follow-up.
  - HBsAg loss rate (Proportion of results that are Target Not Detected versus Target Detected) at Week 16 of treatment and Weeks 20, 28 and 40 of follow-up
  - Relapse rate HBsAg (% patients who became negative [HBsAg < LLOQ], then increased with HBsAg > LLOQ) at Week 16 of treatment period and Weeks 20, 28 and 40 during follow-up period

---

 Breakthrough is defined by quantifiable HBV DNA increase of  $\geq 1 \log_{10}$  HBV DNA copies/mL above LLOQ. Breakthrough samples will be further assessed for resistance assessments, including both for the nucleos(t)ide analogue as well as for EYP001a (e.g., sequence analysis of FXR response elements in HBV genome). Details will be described in the Laboratory manual. Also refer footnote no. 9 below.

- Virologic failure rate (breakthrough) of HBV-DNA (% patients with a confirmed quantifiable HBV DNA increase of  $\geq 1\log_{10}$  HBV DNA copies/mL above LLOQ) assessed at Week 16 of treatment period and Weeks 20, 28 and 40 during follow-up period
- HBV-pgRNA decline ( $\Delta \log_{10}$ ) from Day 1 to Weeks 4, 8, 12, 16 of treatment period and Week 40 of maintenance period
- HBcrAg decline ( $\Delta \log_{10}$ ) from Day 1 to Weeks 4, 8, 12, 16 of treatment period and Week 40 of maintenance period
- HBeAg quantification for HBeAg pos patients and changes at Week 16 of treatment and Week 40 of follow-up
- Fibroscan VCTE change from screening value to Weeks 16 and 40 or ET value
  
- Safety and Tolerability assessed as:
  - Treatment-emergent adverse events (TEAEs) (including SAEs)
  - All-cause mortality
  - Clinical laboratory tests
  - Pruritus assessment
  - Vital signs (blood pressure, heart rate, respiratory rate, and temperature)
  - Concomitant medications
  - Physical examinations
  - 12-lead ECG
  
- PK assessed as:
  - Plasma concentration of EYP001a or any relevant active metabolites (as identified in an ongoing phase 1 study)
  
- PD biomarkers:

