### 6.2.1. Screening Evaluations

Patients will be assigned screening numbers (Format: three-digit site number ‘-‘three-digit participant number e.g. 001-001, 001-002, etc.) consecutively by the Investigator or designee at the time the patient signs the ICF. For all patients screened, the Investigator or designee will record the eligibility criteria assessment in the medical record. A screening and enrolment log will capture the screening number for each patient, the date of screening and a screen fail reason(s) for patients that are not eligible to participate.

Enrolment for this study is defined as any patient that has received at least one dose of the investigational product. The enrolment number of the patient will remain the same as the screening number.

Patient who is first designated as a screen failure prior to being randomized may be rescreened upon Sponsor or designee approval. Patients will be randomized into the study once all eligibility criteria are confirmed.

All screening tests must be performed within study Weeks -12 to -1, unless otherwise indicated. Procedures to be performed at Screening Visit includes the following:

- Obtain signed written informed consent prior to screening
- Check patient’s eligibility
- Review and record patient’s demographic details
- Review and record patient’s medical history
- Review and record patient’s prior and concomitant medications
- Perform drugs of abuse screen
- Record patient’s height and body weight
- Calculate body mass index (BMI)
- Perform complete physical examination
- Perform vital signs (systolic/diastolic blood pressure [BP], heart rate, temperature, respiratory rate) evaluation
- Perform AUDIT-C
- Perform clinical laboratory analysis including haematology, serum chemistry panel, coagulation tests, lipid and metabolic profile and TSH.
- Perform serum pregnancy test (for WOCBP only)
- Perform Dipstick urinalysis for all male and female patients
- Perform 12-Lead ECG
- Sampling for analysis of HBV response markers
- Perform Fibroscan VCTE
- Perform Liver imaging (unless done within 6 months prior screening)

All screening Viral serology tests must be performed within study Weeks -12 to -8, unless

---

 For drugs such as amphetamines, methamphetamine, barbiturates, benzodiazepines, cocaine, methadone, opiates, phencyclidine, tricyclic antidepressants and THC (cannabis).

otherwise indicated and test to be performed at Screening Visit includes the following:

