- Perform Viral serology: anti-HIV, anti-HCV, anti-HDV, quantitative HBV-DNA, quantitative HBsAg, anti-HBs, anti-HBe.

Note: all the PD and PK samplings during the study must be performed before study drug administration.

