- Sample for analysis of HBeAg, anti-HBe and anti-HBs will be collected at screening or Day 1, then pre-dose at Week 16, Week 40 (EoS visit) or ET Visit.

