3.2 Key Definitions

The following definitions will be used:

- **Baseline:** The baseline value is defined as the last available valid (quantifiable continuous or categorical value), non-missing observation for each participant prior to first study drug administration. Repeat and unscheduled assessments will be included in the derivation of the baseline values.

For HBsAg, ALT, AST, ALP, and total Bilirubin (TBL), the baseline value is defined as the average of screening and day 1 pre-dose.

For HBeAg, the Baseline value is value taken at screening visit.

- **Change from Baseline:** The change from baseline value is defined as the difference between the result collected/derived at a post-baseline visit/time point and the baseline value.

The change from baseline value at each post-baseline visit/time point will be calculated for all continuous parameters using the following formula:

$$\text{Change from Baseline Value} = \text{Result at Visit/Time Point} - \text{Baseline Value}$$

The change from baseline value will only be calculated if the specific post-baseline visit/time point result and the baseline value for the parameter are both available and will be treated as missing otherwise.

- **Percent Change from baseline:** The percent change from baseline at each post-baseline visit/time point will be calculated for all continuous parameters using the following formula:

$$\% \text{ Change from Baseline} = 100 \times [(\text{Post-Dose Visit Value} - \text{Baseline}) / \text{Baseline}]$$

- **Study day:** The study day of an event is defined as the relative day of the event starting with the date of the first study drug administration (reference date) as Day 1 (there will be no Day 0).

The study day of events occurring before the first study drug administration will be calculated as:

$$\text{Study Day} = (\text{Date of Event} - \text{Date of First Study Drug Administration})$$

For events occurring on or after Day 1, study day will be calculated as:

$$\text{Study Day} = (\text{Date of Event} - \text{Date of First Study Drug Administration}) + 1$$

Study days will only be calculated for events with complete dates and will be undefined for events that are 'Ongoing' at the end of the study.

Relative days compared to an alternative reference point will be calculated similarly, but the alternative starting reference start date will be used instead of the date of the first study drug dosing.

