	Actual Value	Change from Baseline	Actual Value	Change from Baseline	Actual Value	Change from Baseline
Baseline [1]						
N	XX	N/A	XX	N/A	XX	N/A
Mean	XX	N/A	XX	N/A	XX	N/A
SD	XX	N/A	XX	N/A	XX	N/A
Median	XX	N/A	XX	N/A	XX	N/A
Minimum	XX	N/A	XX	N/A	XX	N/A
Maximum	XX	N/A	XX	N/A	XX	N/A
Week 2						
N	XX	XX	XX	XX	XX	XX
Mean	XX	XX	XX	XX	XX	XX
SD	XX	XX	XX	XX	XX	XX
Median	XX	XX	XX	XX	XX	XX
Minimum	XX	XX	XX	XX	XX	XX
Maximum	XX	XX	XX	XX	XX	XX
Week xx						
n	XX	XX	XX	XX	XX	XX
Mean	XX	XX	XX	XX	XX	XX
SD	XX	XX	XX	XX	XX	XX
Median	XX	XX	XX	XX	XX	XX
Minimum	XX	XX	XX	XX	XX	XX
Maximum	XX	XX	XX	XX	XX	XX

Source Listing: 16.2.6.3

SD: Standard Deviation. N/A = Not Applicable.

[1] Baseline is defined as the last valid, non-missing assessment prior to first study drug administration.

Table 14.2.8 Summary of HBcrAg (ITT Set)

Visit	Group 1 (N=XXX)		etc.		Group x (N=XXX)	
	Actual Value	Change from Baseline	Actual Value	Change from Baseline	Actual Value	Change from Baseline
Baseline [1]						
N	XX	N/A	XX	N/A	XX	N/A
Mean	XX	N/A	XX	N/A	XX	N/A
SD	XX	N/A	XX	N/A	XX	N/A
Median	XX	N/A	XX	N/A	XX	N/A
Minimum	XX	N/A	XX	N/A	XX	N/A
Maximum	XX	N/A	XX	N/A	XX	N/A
Week 2						
N	XX	XX	XX	XX	XX	XX
Mean	XX	XX	XX	XX	XX	XX
SD	XX	XX	XX	XX	XX	XX
Median	XX	XX	XX	XX	XX	XX
Minimum	XX	XX	XX	XX	XX	XX
Maximum	XX	XX	XX	XX	XX	XX
Week xx						
n	XX	XX	XX	XX	XX	XX
Mean	XX	XX	XX	XX	XX	XX
SD	XX	XX	XX	XX	XX	XX
Median	XX	XX	XX	XX	XX	XX
Minimum	XX	XX	XX	XX	XX	XX
Maximum	XX	XX	XX	XX	XX	XX

Source Listing: 16.2.6.4

SD: Standard Deviation. N/A = Not Applicable.

[1] Baseline is defined as the last valid, non-missing assessment prior to first study drug administration.

Table 14.2.9 Summary of HBeAg (ITT Set and HBeAg Positive Patients)

Visit	Group 2 (N=XXX)		etc.		Group x (N=XXX)	
	Actual Value	Change from Baseline	Actual Value	Change from Baseline	Actual Value	Change from Baseline
Statistics						
Baseline [1]						
N	XX	N/A	XX	N/A	XX	N/A
Mean	XX	N/A	XX	N/A	XX	N/A
SD	XX	N/A	XX	N/A	XX	N/A
Median	XX	N/A	XX	N/A	XX	N/A
Minimum	XX	N/A	XX	N/A	XX	N/A
Maximum	XX	N/A	XX	N/A	XX	N/A
Week 16						
N	XX	XX	XX	XX	XX	XX
Mean	XX	XX	XX	XX	XX	XX
SD	XX	XX	XX	XX	XX	XX
Median	XX	XX	XX	XX	XX	XX
Minimum	XX	XX	XX	XX	XX	XX
Maximum	XX	XX	XX	XX	XX	XX
Week 40						
n	XX	XX	XX	XX	XX	XX
Mean	XX	XX	XX	XX	XX	XX
SD	XX	XX	XX	XX	XX	XX
Median	XX	XX	XX	XX	XX	XX
Minimum	XX	XX	XX	XX	XX	XX
Maximum	XX	XX	XX	XX	XX	XX

Source Listing: 16.2.6.5

SD: Standard Deviation. N/A = Not Applicable.

[1] Baseline is defined as the HBeAg value at screening visit..

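### The Day 1 HBeAg assay is restricted by anti-HBe status and the SAP accepts only a screening HBeAg baseline, so an HBeAg-positive patient sampled on Day 1, as the protocol permits, has no change value

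*Protocol*

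**What the plan says.** Four rules bear on the HBeAg baseline.

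- **Endpoint.** Protocol 2.2.2 names as a secondary endpoint "HBeAg quantification for HBeAg pos patients and changes at Week 16 of treatment and Week 40 of follow-up". Protocol 7.1 and SAP 2.3.2 and 12 carry the same endpoint.
- **Day 1 assay.** The footnote on HBV response markers in Protocol 6.2.2.1 lists the quantitative pre-dose tests for all subjects, ending with "HBV-pgRNA, HBcrAg and HBeAg (the later only for anti-HBe positives subjects".
- **Timing of the pre-treatment sample.** Protocol 7.1 states: "Sample for analysis of HBeAg, anti-HBe and anti-HBs will be collected at screening or Day 1, then pre-dose at Week 16". Week 40 or the early termination visit follows. Appendix A footnote 16 repeats this. Neither place mentions anti-HBe status.
- **Baseline.** SAP 3.2 states: "For HBeAg, the Baseline value is value taken at screening visit". Mock Table 14.2.9 repeats it ("Baseline is defined as the HBeAg value at screening visit"), and Listing 16.2.6.5 flags the screening row as baseline. No fallback is given. SAP 3.2 also treats change as missing unless both the visit value and the baseline exist.

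Protocol 11.1 has a different general rule: baseline is the last non-missing value before the first dose. SAP section 15, which lists changes from the protocol analysis, does not mention HBeAg baseline.

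**The concern.** There are two separate mismatches. The Day 1 footnote selects patients by the antibody (anti-HBe), although the endpoint is defined by the antigen (HBeAg). And the SAP recognises one visit as the source of baseline where the protocol permits either of two.

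Together they leave a gap. An HBeAg-positive patient first sampled on Day 1 has followed Protocol 7.1, yet any value obtained is not a baseline under the SAP. If that patient is also anti-HBe-negative, the footnote provides for no Day 1 HBeAg result at all. In both cases the Week 16 and Week 40 changes are set to missing. The subgroup is small, especially in the control arm, so a few such patients would matter to the summary.

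**Working it through.** The documents give no figure to reproduce. The check is a trace of the rules, followed by the size of the subgroup.

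**Is HBeAg measured at screening?**

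1. The general list in Protocol 6.2.1 includes "Sampling for analysis of HBV response markers". Appendix A marks that row at screening, and its footnote 16 includes HBeAg in the panel. HBeAg is therefore scheduled at screening.
2. The separate screening serology list ends with "quantitative HBV-DNA, quantitative HBsAg, anti-HBs, anti-HBe" and does not name HBeAg. Alone this shows little, because the marker panel covers it.
3. The timing rule specific to HBeAg, in Protocol 7.1 and footnote 16, nevertheless permits screening or Day 1. Protocol 3.1 lets HBeAg status for stratification come from medical history, so randomization does not require a screening quantification.

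A site can thus stay within the HBeAg timing rule without a screening value, although the schedule points to having one.

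**What happens to each HBeAg-positive patient?**

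| HBeAg sample before treatment | Anti-HBe | Day 1 result under the footnote | SAP baseline | Change at Weeks 16 and 40 |
|---|---|---|---|---|
| Screening | either | not needed | screening value | defined |
| Day 1 only | positive | yes | none | missing |
| Day 1 only | negative | no | none | missing |

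The second row depends only on the SAP rule. In the third row the footnote also removes the value that a fallback would use. How many HBeAg-positive patients are anti-HBe-negative is not stated in the documents.

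**How large is the subgroup?**

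Inputs: an expected HBeAg negative-to-positive ratio of 7/3 (Protocol 4.1), so 3/10 = 0.30 positive; 49 planned patients, 37 and 12 by arm (Protocol 3.1); enrolment suspended after about 25 randomizations (SAP section 15).

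- Planned: 0.30 × 49 = 14.7. By arm: 0.30 × 37 = 11.1 active and 0.30 × 12 = 3.6 control.
- At about 25 randomized: 0.30 × 25 = 7.5. If the 37:12 split holds: 0.30 × 25 × 37/49 = 5.7 active and 0.30 × 25 × 12/49 = 1.8 control.

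One patient is 1/14.7 = 6.8% of the planned subgroup, or 1/7.5 = 13.3% at 25. These are weights of a single patient, not estimates of loss. The number losing a baseline is the number sampled on Day 1 only, which the documents do not give: 0 to all of the subgroup.

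**The case against.** The strongest defence is that the screening schedule already covers HBeAg. The marker panel is due at screening, Protocol 4.1 counts HBeAg status among the values established in the screening period, and Listing 16.2.6.5 expects a screening row. On that reading the SAP chose the visit at which the anti-HBe restriction does not apply, and every patient sampled there keeps a baseline whatever the footnote says. A single visit also gives all patients the same kind of baseline.

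Most of this stands. It means the loss is conditional, and that it may be zero. It does not remove the contradiction, because the HBeAg timing rule explicitly offers Day 1 as an alternative and the SAP has no provision for a patient who used it.

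A reader might infer from the serology list that HBeAg is not measured at screening, or that the HBeAg-positive subgroup as a whole loses its baseline. The documents do not support either: the panel in Appendix A includes HBeAg and is marked at screening. Nor are 15 of 49 or 7 to 8 of 25 counts of affected patients; they are the size of the endpoint population.

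**Conclusion.** The point holds as a contradiction between operative rules with a conditional consequence. The footnote's selector does not match the endpoint population, and the SAP discards a baseline that the protocol allows. The SAP rule also differs from the general baseline in Protocol 11.1 without an entry in section 15.

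The loss is between 0 and all of about 15 patients as planned, or 7 to 8 at about 25 randomized. The upper end assumes the 7/3 ratio holds and every HBeAg-positive patient was sampled on Day 1 only. The lower end applies if the screening panel was done as scheduled.

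The consequence is confined to one secondary endpoint, which Protocol 11.3.3.2 summarizes descriptively and which is not among the inferential analyses in SAP 3.3. A reader might infer that the primary model is affected because it adjusts for HBeAg. It is not: that covariate is positive or negative status, which may come from medical history, and does not use the quantitative baseline.

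**What to change.** 1. In the Protocol 6.2.2.1 footnote, make HBeAg-positive subjects the population for Day 1 HBeAg quantification, to match the endpoint.
2. In SAP 3.2, mock Table 14.2.9 and Listing 16.2.6.5, define HBeAg baseline as the screening value or, if that is missing, the Day 1 pre-dose value.
3. List in SAP section 15 any difference that remains from the last-pre-dose rule in Protocol 11.1. Screening-first ordering is itself such a difference when both values exist.

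The drafting cost is a few phrases, and HBV marker blood is already scheduled pre-dose on Day 1. There are two drawbacks. Baselines may come from two visits up to 90 days apart, so the listing should show which visit was used. And with enrolment suspended, the footnote change cannot recover Day 1 assays that were not run for patients already enrolled; for them the SAP fallback helps only where a Day 1 HBeAg result exists.

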#### 6.2.2.4. Treatment Visit 4 (Week 6 [Day 42 ± 3 days])

The treatment Visit 4 is planned on Day 42 ± 3 days in Week 6. Following activities are planned for the visit:

- Review and record patient's prior and concomitant medications
- Perform vital signs (systolic/diastolic BP, heart rate, temperature, respiratory rate) evaluation pre-dose
- Pruritus assessment
- AE monitoring
- Perform clinical laboratory analysis only liver safety testing: ALT, AST, ALP, GGT, total bilirubin, thrombocytes and albumin
- Sampling for analysis of HBV response markers
- PD biomarker sampling
- PK Sampling
- Review returned patient diary and dispense new diary
- Collect used/unused study drug and assess compliance

#### 6.2.2.5. Treatment Visit 5 (Week 8 [Day 56 ± 3 days])

The treatment Visit 5 is planned on Day 56 ± 3 days in Week 8. Following activities are planned for the visit:

- Review and record patient's prior and concomitant medications
- Record patient's body weight
- Calculate BMI
- Perform symptom-directed physical examination
- Perform vital signs (systolic/diastolic BP, heart rate, temperature, respiratory rate) evaluation pre-dose
- Pruritus assessment
- AE monitoring
- Perform clinical laboratory analysis including haematology, serum chemistry panel, coagulation tests, lipid and metabolic profile and TSH.
- Perform urine pregnancy test (for WOCBP only)
- Perform Dipstick urinalysis for all male and female patients
- Perform 12-Lead ECG
- Sampling for analysis of HBV response markers
- PD biomarker sampling
- Liver fibrosis and inflammation assessment
- PK Sampling
- Review returned patient diary and dispense new diary
- Dispense EYP001a or placebo and NA
- Collect used/unused study drug and assess compliance

#### 6.2.2.6. Treatment Visit 6 (Week 10 [Day 70 ± 3 days])

The treatment Visit 6 is planned on Day 70 ± 3 days in Week 10. Following activities are planned for the visit:

- Review and record patient's prior and concomitant medications
- Perform vital signs (systolic/diastolic BP, heart rate, temperature, respiratory rate) evaluation pre-dose

- Pruritus assessment
- AE monitoring
- Perform clinical laboratory analysis only liver safety testing: ALT, AST, ALP, GGT, total bilirubin, thrombocytes and albumin
- Sampling for analysis of HBV response markers
- PD biomarker sampling
- PK Sampling
- Review returned patient diary and dispense new diary
- Collect used/unused study drug and assess compliance

6.2.2.7. *Treatment Visit 7 (Week 12 [Day 84 ± 3 days])*

The treatment Visit 7 is planned on Day 84 ± 3 days in Week 12. Following activities are planned for the visit:

- Review and record patient's prior and concomitant medications
- Record patient's body weight
- Calculate BMI
- Perform symptom-directed physical examination
- Perform vital signs (systolic/diastolic BP, heart rate, temperature, respiratory rate) evaluation pre-dose
- Pruritus assessment
- AE monitoring
- Perform clinical laboratory analysis including haematology, serum chemistry panel, coagulation tests, lipid and metabolic profile and TSH
- Perform urine pregnancy test (for WOCBP only)
- Perform Dipstick urinalysis for all male and female patients
- Perform 12-Lead ECG
- Sampling for analysis of HBV response markers
- PD biomarker sampling
- Liver fibrosis and inflammation assessment
- PK Sampling
- Review returned patient diary and dispense new diary
- Dispense NA
- Collect used/unused study drug and assess compliance

6.2.2.8. *Treatment Visit 8 (Week 14 [Day 98 ± 3 days])*

The treatment Visit 8 is planned on Day 98 ± 3 days in Week 14. Following activities are planned for the visit:

- Review and record patient's prior and concomitant medications
- Perform vital signs (systolic/diastolic BP, heart rate, temperature, respiratory rate) evaluation pre-dose
- Pruritus assessment
- AE monitoring
- Perform clinical laboratory analysis only liver safety testing: ALT, AST, ALP, GGT, total bilirubin, thrombocytes and albumin
- Sampling for analysis of HBV response markers
- PD biomarker sampling

- PK Sampling
- Review returned patient diary and dispense new diary
- Collect used/unused study drug and assess compliance

